2.2 Relevant preliminary data

A risk communication and surveillance strategy is needed in primary care to ensure that patients are adequately informed about medication risks and are taking prescribed regimens safely. This is most salient for Rx medications the Food & Drug Administration (FDA) has deemed to possess serious public health concerns, warranting a Medication Guide and/or Risk Evaluation and Mitigation Strategy (REMS). To our knowledge, no such strategy exists to support and monitor outpatient medication use in a cost-sustainable manner.

We devised an Electronic health record-based Medication Complete Communication (EMC2) strategy that leverages electronic health record (EHR) and interactive voice response (IVR) technologies to: 1) prompt and guide provider counseling; 2) automate the delivery of Medication Guides at prescribing; 3) engage patients post-visit via IVR to confirm they have sufficient information and are using Rx properly; and 4) activate the clinical team to help patients overcome any barriers to safe Rx use.

Collectively, our team has previously designed and field tested each of the core functions of the EMC2 Strategy components, and is now integrating these tools for this project at our sites:

STU#: 00201638

- Health Literacy, 1-Page Med Guide Summary. Drs. [name] and [name] recently completed a series of investigations, culminating in a randomized trial comparing the effectiveness of 3 different print versions of an improved Med Guide, 1-Page Summary sheet to supplement the longer, FDA-approved document. All versions included plain language (<8th grade level) and varying formats modified to promote information accessibility. 1003 adults were recruited from two outpatient primary care practices. One specific format, referred to as the Health Literacy format consistently demonstrated the highest comprehension scores, and in multivariable analyses, outperformed all others and receipt of the FDA Med Guide alone. The 1-page summary form concept to include with longer Med Guides was recently reviewed and supported at the July 2014 Brookings Institution advisory panel. As part of a recent AHRQ-funded study, we created English and Spanish Med Guide Summaries using the Health Literacy format for 33 medications [R18HS17220].
- EHR Tools to Deliver Patient Medication Information. Drs. [name] and [name] continue to work together on several pilot projects that leverage EHR platforms (EpicCare, Cerner Powerchart, GE Centricity) to standardize prescribing, provide Spanish translations, prompt medication reconciliation before and during clinical encounters, and to automatically generate Med Guide Summaries (Epic, Cerner, Centricity). Med Guide Summaries are embedded in the EHR as PDF documents, linked to medications, and automatically cued to print with the after-visit summary once a prescriber places the order. As each Med Guide Summary was written in active voice, it also serves as a counseling support tool. In prior field tests [R18HS17220; R21CA132771], each PDF Summary had a 'dot phrase' function so a provider could manually access and share content on screen by simply typing the name of the drug and hitting return (i.e. ".REGLAN <ENTER>"). While >85% of the time patients received Med Guide Summaries, the dot phrase commands were too passive as a method for providers to use for counseling. Guided by Alliance clinical staff feedback, the EMC2 now will use a prescriber alert to prompt clinicians and automate a view of the Med Guide Summary, with an option to 'ignore' if desired.
- Training Clinicians on Health Literacy Spoken Counseling Best Practices. Collectively, Drs. [name], [name] and [name] have extensive experience developing and implementing provider and nurse training sessions for brief counseling to support preventive screening, disease management, hospital discharge instructions, and medication education.
- IVR System Linked to EHR. Drs. [name] and [name] have 10+ years' experience developing and evaluating IVR systems in urban populations. They have led the development and evaluation of IVR systems designed to improve health for people with asthma, obesity, spinal cord injury, and primary care for children. Most recently, they have developed and evaluated an integrated, patient-centered health information system - the Personal Health Partner (PHP). The PHP is a fully automated conversational system that uses synthetic speech (TTS), automatic speech recognition (ASR), and a data-driven multimodal conversational system to gather personal health data and counsel parents before scheduled visits. Patient-reported data is then shared with the provider via the EHR (GE Centricity) and combined with decision support and recommendations. Their work with patient-facing IT system development has focused on usability for patients with limited literacy by integrating plain language principles and key informant feedback into the design, testing, and refinement of their systems. As a result, studies have shown that PHP patient use patterns did not vary by literacy level.
- User-Centered Design of Primary Care-based Interventions. The EMC2 Strategy involves clinical staff at performance sites to 'on-board' the intervention at practices. In field tests, our team included clinicians in the design of EHR and IVR tools. Providers reported high (>90%) satisfaction rates; time-motion studies found no differences in time spent in clinical encounters once tools were activated. Drs. [name] and [name] have also been mindful of the manner in which IVR

STU#: 00201638

systems fit into clinical workflow to improve efficiency. As primary care physicians themselves, they are aware of the time pressures and competing demands, and as such, IVR tools are designed with this in mind. For IVR tools, 100% of physicians reported it improved patient care.

2.3 Scientific or scholarly background for, rationale for, and significance of the research based on the existing literature and how it will add to existing knowledge.

The FDA has acknowledged the complexity of Med Guides and is actively investigating ways to improve them and other tangible sources of patient medication information. In July 2014, the FDA sponsored a Brookings Institution public workshop to consolidate health literacy research in this area and identify future directions.

Technological solutions can be leveraged to prompt provider behavior, help patients explicitly learn how to safely take prescribed medications, and monitor medication use at a cost that is not prohibitive to clinics. Our EMC2 Strategy will impart these activities using technologies that are increasingly prevalent per federal mandates (Health Information Technology for Economic and Clinical Health (HITECH) Act), particularly among community health centers. With the EMC2 Strategy, we respond to the Office of the National Coordinator (ONC) 'Meaningful Use' criteria by leveraging an EHR to deliver standard, patient-centered information supporting safe use. In this model of care, we merge the benefits of our research on improving counseling at the point of prescribing ([name], [name]) with our research to monitor and support patients in the most effective, available, and patient-centered manner using an interactive voice response (IVR) system ([name], [name]). This multi-faceted, primary care approach will promote and monitor the use of high risk medications and activate the clinical team to respond to any concerns relating to medication acquisition, proper use, and safety.

IVR vs. Other Technology Outreach Platforms. The longstanding criticism of IVR systems has been the frustration it may cause consumers. In recent years, however, dramatic improvements have been made with the technology, and studies repeatedly demonstrate high accuracy, patient satisfaction, cooperation rates, and patient engagement with IVR tools. In fact, Lyles et. al. found no differences by literacy, race/ethnicity, or language for pattern of use of their IVR system. Other options for monitoring patients post-visit were considered for the EMC2 Strategy (i.e. text messaging, smartphone applications, web-based EHR portal), however, we found these had serious limitations. In a recent study by our team examining health technology use among primary care patients (N=1,077), we found those with low literacy skills were significantly less likely to own a cell or smart phone or have access to high speed internet compared to those with adequate literacy. Among those that did, lower literate patients were less likely to send/receive texts or use the internet to communicate with healthcare providers (in press, Health Expectations). Similar differences were found by patient age, leading us to believe that older patients and those with limited literacy would be marginalized if our strategy utilized mobile or web portal platforms. In contrast, IVR works with landlines and mobile phones, capturing >90% of low literate and elderly audiences. It offers a simple interface that is usable by a broad range of patients including patients with low literacy and the elderly, and can now connect to an EHR to share results with providers. It was therefore a clear choice for our primary care-based EMC2 strategy, which will: 1) increase provider counseling at the time of ordering a higher-risk drug, 2) increase the frequency of patients receiving easy-to-understand, actionable information describing safe drug use, risks and warnings, 3) improve patients' understanding and demonstrated proper use of their medication, and 4) increase the rate of timely detection of an ADE or other medication-related concern.

3. INCLUSION AND EXCLUSION CRITERIA

STU#: 00201638

3.1 Methods of screening for eligibility

Patients will be initially screened for eligibility by Alliance's data pull and further screened over the phone by Northwestern Research Assistants (RAs).

Screening by Alliance. Alliance will send information to Northwestern on patients who meet the following conditions: (1) newly prescribed (i.e. had not been prescribed at Alliance within the previous two years) one of our study medications, (2) preferred language listed as English or Spanish, (3) age as of clinic visit > 21 years, (4) clinic visit occurred at a participating health center location (7 clinics associated with Near North Health Services Corporation).

Screening by Northwestern. Northwestern Research Assistants (RAs) will call those patients identified by Alliance and further screen them by asking eligibility questions and screening for cognitive impairment, in alignment with the inclusion and exclusion criteria (3.2).

We will receive patient information from Alliance in one of two ways:

Method 1- Each morning, Research Assistants (RAs) at Northwestern University will be able to access an SSRS report on a secure platform (Alliance SharePoint) showing a list of patients triggered as potentially eligible during a clinic visit on the day prior. The report will show the patient's contact information necessary for outreach for the purpose of screening (record id, first and last name, date of birth, clinic name, phone number, preferred language, and date of index clinic visit), but will not include the patient's medication information necessary for conducting the baseline interview. The RA will then call each patient, ask the few remaining eligibility questions to complete the screening process, invite the patient to participate, and obtain informed consent over the phone. The RA will then schedule a time to call the patient back for the baseline interview the next day (or as soon as possible thereafter). At the end of each day, the RA will upload a list of newly consented patients to Alliance Sharepoint, prompting Alliance to send medication information for those patients the following morning.

Method 2- Each morning, Research Assistants (RAs) at Northwestern University will receive, via file sent to a secure ftp site, a list of patients triggered as eligible during a clinic visit on the day prior. The report will show the information needed to contact the patient and conduct the baseline interview (same data as listed in method 1, plus the name(s) of any study medications prescribed during the visit, the associated sig(s), prescriber name, and regular physician name). With this method, RAs will be able to conduct the baseline interview during the same phone call, immediately after screening and consenting the patient. This method would also allow the RA to explain to the potential participant which of their prescribed medicines would be the subject of the interviews and to confirm that the medication was actually prescribed, eliminating any confusion.

STU#: 00201638

Automatic exposure to part of intervention. Clinics will be randomized either to the intervention arm or to usual care. All patients who see a prescriber at a clinic site randomized to the intervention arm and who receive a prescription for one of the study medications (Table 1) will automatically receive some components of the intervention during their clinic visit (provider counseling, Med Guide Summary), regardless of whether or not they meet further screening criteria. This randomization and recruitment process will ensure that recruited patients may receive all in-clinic EMC2 components on the day they receive a prescription for a study drug. It will also result in a trickle down of some components of the EMC2 Strategy being given to patients seen at the intervention clinic site, but not enrolled in the study for follow-up purposes (EHR tools, but not IVR or nurse follow-up). This specific strategy of “turning on” an EHR intervention with provider or clinic level randomization has been previously approved by the IRB at Northwestern University for three other AHRQ funded grants [P01HS021141-01, 1U19HS021093-01 & 1R18HS017220-01]. Prescribers at these intervention sites will be made aware that the EHR tools have been activated, with the understanding that the tools themselves are educational in nature and will have minimal, if no effect on patient care and clinic workflow.

3.2 Inclusion and exclusion criteria

Inclusion Criteria (Patients). To be eligible to enroll in the study, patients must attend one of the seven randomized clinics associated with the Alliance-affiliated health center Near North Health Service Corporation. They must also meet all of the following criteria: 1) age 21 and older; 2) English or Spanish speaking; 3) have received a new or changed prescription (i.e. had not been prescribed at Alliance within the previous two years) for one or more of our study medications (Table 1); 4) have a personal phone line (land or mobile).

Inclusion Criteria (Providers). To be eligible to complete the provider survey, providers must see patients at one of the three Near North clinics randomized to the intervention arm (Louise Landau, Komed Holman, Sunnyside).

Study medications. To select these drugs, we reviewed the top prescriptions ordered in 2013 by providers at Alliance FQHCs and selected those that have a Med Guide/REMS requirement. These drugs were reviewed by clinicians and pharmacists to ensure the list was comprehensive and appropriately reflects prescribing behaviors in the clinics. These drugs are diverse by class, indication, duration, side effects, route of administration, and potential for harm. Each has an FDA risk communication goal that presently is not being achieved.

Table 1.

STU#: 00201638

testosterone	escitalopram	sitagliptin and metformin
amiodarone	fluoxetine	exenatide
carbamazepine	paroxetine	liraglutide
divalproex	sertraline	pioglitazone
gabapentin	doxepin	rivaroxaban
lacosamide	imipramine	ciprofloxacin
lamotrigine	mirtazapine	levofloxacin
levetiracetam	colchicine	moxifloxacin
oxcarbazepine	emtricitabine and tenofovir	salmeterol
phenytoin	nevirapine	budesonide and formoterol
pregabalin	fenofibrate	fluticasone and salmeterol
topiramate	clopidogrel	celecoxib
valproic acid	alendronate	diclofenac
aripiprazole	risedronate	indomethacin
quetiapine	pimecrolimus	meloxicam
clonazepam	tacrolimus	sulindac
bupropion	amphetamine	dexlansoprazole
trazodone	methylphenidate	pantoprazole
desvenlafaxine	linagliptin	metoclopramide
duloxetine	saxagliptin	tamoxifen
venlafaxine	saxagliptin and metformin	varenidone
citalopram	sitagliptin	propylthiouracil

alprazolam	ibandronate	mometasone-formoterol
apixaban	lisdexamphetamine	nortriptyline
dexmethylphenidate	lorazepam	olanzapine
diazepam	lurasidone	tramadol
fluticasone-vilanterol		

Table 1 – part 2.

Exclusion criteria. Subjects will be excluded from the study if any of the following conditions are met: 1) Aged <21 years, 2) non-English or -Spanish speaking, 3) any severe, uncorrectable vision, hearing or cognitive impairments (measured by the six-item screener) that would impede study interviews, 4) unable to complete follow up interviews.

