9.2 Description of the intervention

1. Provider Medication Alert: If a prescribing clinician attempts to place a new order or change an existing prescription for one of the study medications (Table 1), an EHR-generated alert will notify the provider that the medication requires patient counseling. This alert will contain a brief description of the top risks or side effects that patients may experience while taking this medication; this information is directly derived from the FDA-approved Medication Guide for the drug. The pop-up will also include an html link to the 1-page Med Sheet, which they can use to further inform their counseling.

2. Automated Delivery of Med Guide Summary: When the patient leaves an encounter and checks out, the medication order in Centricity will automatically cue printing of the 1-page Med Guide Summary.

STU#: 00201638

3. IVR Follow-Up Phone Assessment: One day after a patient's baseline interview (which will occur within 1-30 days post-visit), the patient will be prompted to call into the automated IVR system. The goal of the IVR call is to confirm patients' understanding and safe use of the prescribed high-risk medication they are taking, and to screen for any adverse drug events that may arise from having taken the medicine.

The call will investigate content areas that will be standard across all medications under study: 1) medication recognition, 2) medication fill (and fill barriers, if applicable), medication adherence (and adherence barriers, if applicable), perceived effectiveness, and side effects experienced. The IVR content was derived from the Med Guide Summaries. Patients are able to speak their responses as "yes", "no", or "do not know" or use their keypad.

To facilitate the call, patients will be sent (via text or phone call) a call-in number for the IVR system so that they are able to make the call at their convenience. The text with the call-in number will be sent on the day following the patient's baseline interview. (The day lag is needed so that the participant's medication data can first be uploaded to the IVR system in preparation for the call).

If subjects have not used the system after one day, a reminder text message, again including the call-in number, will be sent by the RA at Northwestern. If subjects have not used the system after two days, the RA at Northwestern will call the patient to remind them to call into the system and to ensure they have the call-in details.

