Time-sensitivity: Subjects become eligible at the time they are newly prescribed one of the study medications, with primary outcomes including their proper understanding and use of the medication, near to the time of fill and for the following 3 months. Therefore it is imperative that we are able to recruit them within the first week of their new prescription to launch the intervention. Receiving data from the EHR to identify and recruit eligible patients and consenting via phone is the only viable solution given the time constraints of the intervention. The IVR intervention call is triggered from completion of baseline (as early as 1 day after the baseline interview and within 4 weeks of the clinic visit), with the aim to reinforce learning and identify medication errors, including serious side effects. Given the range in duration of the medications included, including a number of short duration medications, it would not be possible to wait for a written HIPAA consent to be mailed by participants. It is imperative that the IVR functions while participants are currently taking the medications to accurately capture side effects and medication issues.

Resource limitations: While we did consider the possibility of on-site recruitment or leveraging clinic staff to support consent and/or data collection efforts, this is not possible. Working within the confines of the financial limits of the R01 mechanism, we cannot afford the resources to have staff in all of the 12 geographically diverse locations. Potentially eligible patients cannot be pre-identified, as patients only become eligible once they are prescribed a medication from the study list. It would also be too great a burden to ask clinic staff to remember to disperse a consent form and written HIPAA at the time of prescribing (this has been discussed with clinic sites), and an alert cannot also be included to that regard. Asking clinic staff to distribute consent forms would also require all staff at each clinic site to become research study personnel authorized to consent participants. Training each nurse and care coordinator who could potentially interface with patients once triggered would be an impossible task, especially given the shift-work nature of these positions. Any other efforts to have the patient provide written HIPAA consent would place undue burden on the patient for participating.

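### Inclusion criterion 3 needs one consistent wording, and use of the study drug before the index visit should be recorded and adjusted for, because the look-back sees only Alliance orders

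*Combined protocol and SAP*

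**What the plan says.** All references are to the combined protocol and SAP.

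- **Criterion (3.2).** Patients must "have received a new or changed prescription (i.e. had not been prescribed at Alliance within the previous two years". The age limit is 21 and older, and the exclusion criteria remove only those under 21.
- **Data pull (3.1).** Alliance sends patients "newly prescribed (i.e. had not been prescribed at Alliance within the previous two years) one of our study medications". It also requires "age as of clinic visit > 21 years". Only patients on this list are called.
- **Phone screen (3.1).** The research assistant is to "ask the few remaining eligibility questions to complete the screening process", in line with 3.2. Nothing in 3.2 concerns the same drug obtained elsewhere.
- **Population (section 29).** "Subjects become eligible at the time they are newly prescribed one of the study medications".
- **Alert (9.2).** It fires when a prescriber "attempts to place a new order or change an existing prescription for one of the study medications".
- **In-clinic exposure (3.1).** At intervention clinics, patients who see a prescriber and "receive a prescription for one of the study medications (Table 1) will automatically receive some components of the intervention" do so "regardless of whether or not they meet further screening criteria".
- **Data on prior use.** Neither the baseline covariates in 9.4 nor the potential confounders in 11.1 include earlier use of the index drug. Section 25.3 gives the research team no access to medical records.

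**The concern.** There are two separate issues.

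The first is wording. 9.2 shows that in this protocol a change can mean a change to a prescription already running. A patient whose Alliance prescription was written last year and is altered today is eligible on the leading words of criterion 3 and ineligible on the definition that follows them. Anyone reporting the trial population would have to choose between the two.

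The second matters more for the analysis. The two-year rule looks only at Alliance orders. A patient who has taken the drug for years from a hospital or another practice, and now gets a first Alliance order, satisfies it. Proper use is scored on indication, dose, frequency and daily total (9.4), and knowledge on decisions before use, risks and benefits, and side effects. An established user may already know much of this and so have less to gain. Mixing such patients in would pull both arm differences towards zero. With seven clinics, three of them in the intervention arm, their share could also differ between arms by chance. If prior use is not recorded, the analyst can neither see such a difference nor correct for it.

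**Working it through.** **Step 1: compare the rules.**

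| Place | New Alliance order, none in two years | Change to an Alliance prescription under two years old | First Alliance order, drug already taken from elsewhere |
|---|---|---|---|
| 3.2, leading words | in | in | in |
| 3.2, two-year definition | in | out | in |
| 3.1, data pull | in | out | in |
| 9.2, alert (exposure only) | fires | fires | fires |

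The second patient column shows the contradiction inside 3.2. The pull resolves it in practice, because such a patient is never sent to the research assistant. The third column is the real gap: every rule that governs enrolment lets this patient in.

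**Step 2: look for another control on prior use.** The inclusion and exclusion lists (3.2), the measures (9.4), the confounders (11.1) and data access (25.3) contain none. The nearest items are number and type of medications and previous history with side effects (11.1). They may correlate with prior use but do not measure it.

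**Step 3: reproduce the plan's power figure.** Inputs from 11.2: 480 per arm at 3 months, SD 28.4, ICC 0.001, 80 per site, two-sided 5%, difference 5.5.

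- Design effect = 1 + (80 − 1) × 0.001 = 1.079.
- SE = 28.4 × √(2 × 1.079 / 480) = 1.904.
- Detectable difference at 80% power = (1.960 + 0.842) × 1.904 = 5.33, against the stated 5.5.
- Power for 5.5 = Φ(5.5 / 1.904 − 1.96) = 82%, against the stated 80%.

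The plan's figure is slightly conservative on its own inputs.

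**Step 4: scale the dilution.** Let f be the share of experienced users. The documents do not give f, so 10% to 30% is an assumption. The average effect is 5.5 × (1 − f) if they gain nothing and 5.5 × (1 − f/2) if they gain half as much. Power = Φ(effect / 1.904 − 1.96).

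| f | Effect, half gain | Power | Effect, no gain | Power |
|---|---|---|---|---|
| 0% | 5.50 | 82% | 5.50 | 82% |
| 10% | 5.22 | 78% | 4.95 | 74% |
| 20% | 4.95 | 74% | 4.40 | 64% |
| 30% | 4.67 | 69% | 3.85 | 52% |

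**Step 5: scale an imbalance.** Bias = (difference in share between arms) × (knowledge advantage of experienced users). Neither factor is in the documents. If the shares differ by 10 percentage points, an assumed advantage of 5, 10 or 15 points gives a bias of 0.5, 1.0 or 1.5 points. That is 9%, 18% or 27% of 5.5.

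**Step 6: age.** The pull requires more than 21, whereas 3.2 admits 21. If the query works in whole years, every eligible 21-year-old is missed. If it works in exact age, only a visit on the 21st birthday is affected.

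**The case against.** The strongest reply is that criterion 3 works as intended. The two-year definition is worded the same way in 3.1 and 3.2, the pull applies it before anyone is called, and the word *changed* therefore admits almost nobody. This stands, and it reduces the contradiction to a matter of wording. It does not touch the Alliance-only look-back, because the pull itself has that limit.

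It can also be said that a first order in this record system is a sensible trigger for a strategy that runs from that system, and that the aims in 1.1 are not restricted to drug-naive patients. That is fair, and it is a reason not to exclude experienced users. It is no reason to leave them unidentified.

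The power loss rests on an assumed share. The no-gain case is extreme, since section 2.1 describes poor risk knowledge and poor Medication Guide comprehension among patients generally. The calculation also takes 5.5, stated as a minimum detectable difference, as the true effect in new users, and it uses the 12-location layout of 11.1 although 3.1, 3.2 and 19.1 have seven clinics. All of this stands. The figures give a scale, not an estimate.

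Chance imbalance between a few clinics can affect any covariate. That is true, but most of the others are measured.

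Two further criticisms might be inferred and do not hold. The alert in 9.2 is broader than enrolment, but 3.1 and 9.1 say this is deliberate, and it leaves no enrolled patient unexposed. Under Method 1 the research assistant screens before knowing the drug, but the criterion as written is applied by the pull and does not need that knowledge.

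**Conclusion.** The point holds in two parts. The wording of criterion 3 conflicts with its own definition and with 3.1 and section 29, and should be reconciled; the practical effect is probably small because the pull decides who is called. The larger matter is that experienced users from outside Alliance can enter as new users, with no listed item that records this and no planned adjustment for it.

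The expected consequence is dilution of the knowledge and proper-use differences, since the rule is the same in both arms. Bias would need unequal shares, which is possible with seven clinics but not shown. The size cannot be fixed from the documents. Under an assumed share of 10% to 30%, power falls from about 82% to 78–69% with half the gain, or to 74–52% with none.

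A reader might infer that the words *or changed* bring current Alliance users into the trial, or that the trial is underpowered for this reason. The documents support neither: the pull blocks the first, and the second depends wholly on an assumed share and an assumed loss of benefit. This is a worthwhile, inexpensive correction and not a fatal flaw. The age difference between pull and criterion is a minor inconsistency that can omit eligible patients.

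**What to change.** 1. Use one definition of an eligible prescription in 3.1, 3.2 and section 29, and say explicitly whether an altered prescription qualifies. The alert in 9.2 can stay as it is.
2. Add one item to the baseline interview in both arms, when the drug name is known under either method: had the patient taken this medicine, from any source, before the index clinic visit? The question must refer to the time before the visit. By 9.2 the baseline interview may come up to 30 days afterwards, when true new users may already have started.
3. Do not exclude on the answer. It is given after clinics are randomised and after in-clinic exposure, so exclusion could select patients differently by arm.
4. Prespecify prior use as a covariate in the knowledge and proper-use models of 11.1, with a sensitivity analysis restricted to new users. Report the share by arm and clinic.
5. Set the data pull to age 21 or over.

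The cost is one interview item, a wording edit and a query change. Recall of earlier use is imperfect and may differ somewhat by arm, because intervention patients have already been counselled and given a drug sheet. For that reason the new-user analysis should remain a sensitivity analysis.
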